Cover Page

Study Title

“Implementation of a Shared Decision-Making Aid for Reducing Stigma against Drug Use and HIV Harm Reduction in a Rural Setting”

Identifiers: NCT05352412

Unique Protocol ID: 202107155

Date: March 25, 2022

Study Protocol

Project Title:

Implementation of a Shared Decision-Making Aid for Reducing Stigma against Drug Use and Harm Reduction in a Rural Setting

Select how you plan to obtain consent:

- Letter or information sheet with no signature
- Script for use either in person or over the phone with no signature

Summary:

Patients who inject drugs are at high risk for invasive bacterial and fungal infections related to contaminated needles. These patients should be treated with a combination of antibiotics and addiction treatment. Our team has demonstrated that medications for opioid use disorder (MOUDs; e.g., methadone, suboxone), improve patient outcomes. However, there is substantial stigma associated with these medications. Both patients and healthcare providers view them as drugs for "addicts." The goal of this proposal is to determine if a shared decision aid to help patients select the most appropriate MOUD will reduce internal stigma by the patient (reluctance to start on MOUDs) and stigma from the healthcare provider to offer a prescription for MOUDs. We propose to use serial stigma survey assessments before, directly after, and weeks after use of the tool.

Specify your research question(s), study aims or hypotheses:

We hypothesize that the use of the tool will reduce healthcare and patient stigma about use of MOUDs.

Background and significance and/or Preliminary studies related to this project:

In the past decade, the US opioid crisis has emerged as a leading cause of death among adults. It has also led to an increase in invasive bacterial and fungal infections; and HIV and HCV outbreaks in multiple regions. Rural communities have had an especially disproportionate burden from the impact of opioid use disorder (OUD). Treatment of OUD with pharmacotherapy is one of the most effective strategies for reducing OUD related mortality and morbidity. But while there has been increasing will for expanding pharmacotherapy, stigma – from community, providers and patients—remains a significant barrier to uptake pharmacotherapy and harm reduction. The approach to substance use has historically favored abstinence strategies that are often without evidence, influenced by punitive, stigmatizing framework. This stigma may be even more prevalent in rural communities. To date there have been very few effective interventions to address inter- and intrapersonal stigma, and none with sustained effectiveness.

Describe EACH of your participant populations

We will have 2 patient populations.

1) Healthcare providers.

Inclusion criteria:

-physician, nurse practitioner, or physician assistant with a DEA X waiver to prescribe MOUDs

- provides care to patients at Barnes-Jewish Hospital
- must be able to complete electronic survey written in English

2) Patient inclusion criteria

- patient from a rural community currently admitted or recently admitted to Barnes-Jewish Hospital
- Admission must be for an infection associated with intravenous drug use
- Patient must be willing to speak with healthcare provider about MOUDs
- patient must be over 18 years old
- must be able to complete electronic survey written in English

Describe where the consent discussion will occur (check all that apply):

- Private room or area
- By phone

Participants and/or their legally authorized representative will have (check all that apply to the consent process and explain process in Question 1.12 below):

- As much time as they desire to consider enrolling in the study, including:

An opportunity to thoroughly review the consent materials with knowledgeable members of the research team, and with family and/or friends as appropriate

- Sufficient time to have all of their questions answered

Provide a description of the enrollment and consent process in sequential order and address EACH of the bulleted points below:

Study population: We will have 2 study populations. Patients who receive MOUDs and healthcare providers who prescribe MOUDs. These populations will be randomized to either receipt or no receipt of the shared decision tool.

Recruitment: We will send an email to healthcare providers who prescribe MOUDs in the hospital. This will likely include addiction medicine services, internists, emergency medicine providers, psychiatrists, and infectious diseases physicians. We will send the email to people in these divisions. We will also notify staff in the Washington University Bridge to Health Program via email. These individuals include a case manager and 2 health coaches who care for persons who inject drugs as part of a quality improvement project. If these individuals identify a suitable candidate, they will contact our study coordinator or the PI that it is acceptable to approach the healthcare provider and/or patient for study recruitment. The study coordinator will discuss the study either in person or over the phone with the healthcare provider and in person with the patient. The study coordinator will discuss the risks and benefits of enrolling in the study and consent the patient.

Time to consider participation: patients and healthcare providers will have as much time as they need to consider participation. However, ideally, they should start this intervention prior to initiating a MOUD in the hospital.

Minimize coercion: our study coordinator is a trained staff therapist who will inform the participant that the study is completely voluntary and participation will not impact clinical care.

Provide a detailed description in sequential order of the study procedures following the consent process - DO NOT cut and paste from the Consent Document.

This decision aid is a web-based survey that is presented on a tablet. It includes five sections: (D1) Provide an overview of both the disease and treatment. (D2) Assess the patient's eligibility for pharmacotherapy. (D3) Compare the current medication options (methadone, buprenorphine, and long-acting naltrexone), examining demand characteristics, such as side effects, route of administration, and cost. (D4) Describe expectations for treatment duration and effects if the medication is self-discontinued. (D5) Complete a brief values clarification exercise.

After Alpha and beta testing are completed in Aim 1 of this project: After the patient meets with a member of the Bridge To Health team, they will be referred to a member of the research team. The research team member will approach the patient and their provider of medication-assisted treatment once the patient has been stabilized to determine the patient's interest in treatment for their opioid use disorder, but prior to discharge from the hospital. This will usually occur within 2 weeks of the patient being discharged from the hospital. If a patient is interested in participating, consent will be obtained from the patient and their healthcare provider will be approached for consent as well. Once consent from both parties, patient and provider, is obtained the patient will be randomized to either receive the shared decision aid or standard of care. If randomized to receive the shared decision aid, the patient and provider will take the survey on separate devices but at the same time. The decision aid survey integrates a values clarification exercise and summarizes patient concerns/preferences to guide shared decision-making with clinicians. We will measure stigma and other outcomes prior to discharge, 2 weeks post-discharge, and 3 months post-discharge to assess the feasibility and preliminary effectiveness of the decision aid. If the patient is not randomized to receive the decision aid tool, they will complete the survey and receive standard of care. We will measure stigma and other outcomes prior to discharge, 2 weeks post-discharge, and 3 months post-discharge to assess the feasibility and preliminary effectiveness of standard of care.

We will implement a method to create a unique patient ID code to link participant data and information to rather than their name, and that the study team will not collect or record any identifiable health information in order to protect participants' confidentiality

What have you done to minimize any risks?

- Adverse event monitoring

What are the potential benefits related to this project for:

The patient will have more input on what type of MOUD they will receive. This might increase adherence.

The tool may help reduce stigma and improve long-term MOUD acceptance, which will reduce overdose rates among persons who inject drugs.

Provide a summary of the analysis methods you will use, including, if applicable, the data points or outcomes you will analyze.

We will use likert scale questions to assess stigma immediately before and after the survey. We will also measure long-term stigma changes compared to baseline at 2 weeks and 3 months. These results will be compared to the baseline testing results in a paired manner. We will use non-parametric tests to evaluate for statistical significance. We will also compare overall response rates between those who did vs. did not receive the clinical decision tool.

Provide the rationale or power analysis to support the number of participants proposed to complete this study.

This is a pilot study. No power analyses needed.

Participants

18 years old. No age limit. We will not recruit non-English speaking people. Must have diagnosis of opioid use disorder and come from a rural location.

Sites:

Barnes-Jewish Hospital

Privacy and Confidentiality:

Only minimum necessary information to be collected. Recruit in a private setting when possible. Materials will be stored in a secured environment and team members will be the only ones with access.

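### The stated stigma tests do not use the randomisation: only paired comparisons with baseline are planned, and the ambiguous word 'survey' leaves the control procedure and in-hospital time points unclear

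*Combined protocol and SAP*

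**What the plan says.** The hypothesis is comparative in intent: "We hypothesize that the use of the tool will reduce healthcare and patient stigma about use of MOUDs". The enrollment and consent section makes the trial randomised: "These populations will be randomized to either receipt or no receipt of the shared decision tool".

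The study procedures section defines the intervention with the words "This decision aid is a web-based survey that is presented on a tablet". For the aid arm it says "If randomized to receive the shared decision aid, the patient and provider will take the survey on separate devices", and it then names the same object again: "The decision aid survey integrates a values clarification exercise". For the other arm it says "If the patient is not randomized to receive the decision aid tool, they will complete the survey and receive standard of care".

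On timing, the Summary says "We propose to use serial stigma survey assessments before, directly after, and weeks after use of the tool". The study procedures section instead schedules stigma and other outcomes "prior to discharge, 2 weeks post-discharge, and 3 months post-discharge to assess the feasibility and preliminary effectiveness of the decision aid". It repeats the same three time points for controls, with standard of care in place of the aid.

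The analysis-methods section has Likert stigma items answered on either side of 'the survey', and again at 2 weeks and 3 months. Results are compared with baseline in a paired way, using unnamed non-parametric tests. The section closes by saying that overall response rates will be compared between those who received the tool and those who did not. The power section calls the study a pilot and gives no sample size.

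**The concern.** There are two linked problems.

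The first is that one word covers two instruments. A coordinator who followed the study procedures section to the letter would show controls the decision aid, which would largely remove the randomised contrast. If the word means the stigma questionnaire in that sentence, the control procedure is sensible. The reader then still cannot tell at which in-hospital moments controls answer it.

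The second is more important and does not depend on how the word is read. A paired comparison with baseline asks whether scores moved. It does not ask whether they moved because of the aid. Being asked the same questions again can shift scores. So, over the weeks after discharge, can recovery and ordinary care. A concurrent randomised control group is the means of removing such influences, and this trial has one. The plan does not say that it will be used for stigma.

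**Working it through.** **Step 1: what 'survey' refers to.** The word appears 8 times.

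- Decision aid, 4 uses: three in the study procedures section (the definition, the aid-arm instruction and the named decision-aid survey), and one in the analysis-methods section, where the aid is the most sensible reading but is not stated.
- Stigma instrument, 1 use: the Summary.
- Unspecified, 3 uses: two in the inclusion criteria, and the control sentence.

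4 + 1 + 3 = 8. Within the study procedures section, every identifiable use before the control sentence means the aid, so the literal reading is the aid. Against it stand the receipt or no-receipt randomisation and the standard-of-care label in the same sentence. The questionnaire is therefore the likelier meaning.

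**Step 2: when stigma is measured, by arm.**

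| Section | Aid arm | Control arm |
|---|---|---|
| Summary | before, directly after and weeks after using the tool | not stated; controls do not use the tool |
| Study procedures | one pre-discharge point, 2 weeks, 3 months | the same three points |
| Analysis methods | either side of 'the survey', then 2 weeks and 3 months | arm not specified |

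The sections differ in the in-hospital points, but no section gives the two arms different schedules. The single pre-discharge point is not placed before or after the aid, and the schedule has no separate baseline. If that point fell after the aid and served as baseline, later changes would leave out any immediate effect. The text does not exclude this.

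**Step 3: what the stated tests estimate.** Let τ be the effect of the aid on the change in stigma score, and δ the change that would have happened anyway.

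- Mean change from baseline, aid arm: δ + τ.
- Mean change from baseline, control arm: δ.
- A paired test in the aid arm examines δ + τ = 0.
- A paired test in the control arm examines δ = 0.
- A between-arm test of change examines (δ + τ) − δ = τ.

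Only the last addresses the hypothesis, and it is not stated for stigma at any time point. Finding one arm significant and the other not would not replace it.

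**Step 4: illustration on assumed inputs.** The plan gives no sample size, SD, significance level or expected drift, so it contains no figure to reproduce. The assumptions are: normal change scores with SD 1 (a simplification of Likert scores), τ = 0, the same drift δ in both arms, two-sided 5% tests, and 4,000 simulated trials per setting. The table shows the share of trials with a significant result.

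| n per arm | Paired Wilcoxon, aid arm: δ = 0 | δ = 0.2 | δ = 0.3 | δ = 0.5 | Between-arm Mann-Whitney, all δ |
|---|---|---|---|---|---|
| 10 | 4.4% | 8.5% | 13.5% | 28.1% | 4.1% to 4.6% |
| 20 | 4.8% | 13.2% | 23.8% | 54.8% | 4.7% to 5.3% |
| 30 | 4.8% | 18.4% | 35.3% | 73.6% | 4.3% to 5.6% |
| 50 | 5.0% | 27.4% | 52.5% | 92.3% | 4.8% to 5.2% |

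With no drift, both tests hold their level. With drift, only the between-arm test does. This is a general property of the two tests, and the argument in step 3 does not rest on it.

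**The case against.** The strongest reply has four parts.

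- **Control measurements.** A reader might infer that controls have no immediate second measurement, so that the immediate change is certainly an uncontrolled before-after result. The documents do not support that. The analysis-methods section does not restrict the before-and-after items to one arm, and controls are said to complete a survey. The study procedures section also omits a separate directly-after point for the aid arm, where the Summary plainly plans one. Its silence about controls is therefore not evidence of absence. This part stands: the matter is unsettled, not decided against the plan.
- **Response rates.** That comparison closes a paragraph about Likert stigma items and may be meant as the between-arm stigma comparison. This is possible, so the fair criticism is that the term is undefined. As written, it does not identify stigma change as the outcome.
- **The immediate interval is short.** Ordinary inpatient care has little time to act between two measurements on either side of the aid, which leaves mainly repeat questioning. This stands for the immediate point. It does not help at 2 weeks and 3 months, where there is more time for other influences and the same paired-only analysis applies.
- **It is a pilot.** That may excuse the missing power calculation. But the plan proposes significance tests and speaks of preliminary effectiveness, and a pilot also needs a clear control procedure.

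**Conclusion.** The point holds in this form. The control instruction is ambiguous, the in-hospital time points differ between sections, and the only stigma tests stated are paired comparisons with baseline, at every time point. The plan therefore does not state a stigma analysis that uses the randomisation to answer its own hypothesis. It should be fixed, and preferably before data are collected, because a control questionnaire that was never given cannot be recovered later.

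Two stronger readings should be resisted. One is that controls are meant to receive the aid: the wording permits it, but the randomisation statement and the standard-of-care label make it unlikely. The other is that the simulated error rates measure the harm to this trial: drift, SD and sample size were all assumed, and nothing in the documents shows that any drift will occur. No trial-specific size can be given.

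The conclusion assumes only that the analysis-methods section lists all the planned stigma tests and that response rates cannot be taken, undefined, to mean change in stigma.

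**What to change.** 1. Use two terms throughout: 'decision aid' and 'stigma questionnaire'. State that controls are not shown sections D1-D5.
2. Reconcile the in-hospital time points of the Summary, study procedures and analysis-methods sections. Give the stigma questionnaire at baseline, before randomisation, in both arms.
3. Make the stigma comparison a between-arm non-parametric test of change from baseline (for example Mann-Whitney) at 2 weeks and at 3 months. Apply it at the immediate point too if controls answer again after a matched interval. If they do not, label the immediate change a descriptive, aid-arm-only result.
4. Define the response-rate comparison: what counts as a response, and at which time.
5. Analyse patients and providers separately. The study procedures section randomises the patient, and nothing limits a provider to one patient. The provider analysis must therefore allow for anyone who takes part with several patients or in both arms, since a simple two-group test would treat their answers as independent.

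Cost: wording, a little more analysis, and at most one short extra in-hospital questionnaire for controls. Labelling the immediate change descriptive avoids that extra questionnaire.

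### Provider stigma has no specified controlled comparison: no stigma assessment is expressly assigned to providers of standard-of-care patients, and stigma is tested only as paired change from baseline

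*Combined protocol and SAP*

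**What the plan says.** The combined protocol and SAP has no numbered sections, so places are given by topic.

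- **Hypotheses.** Both populations are covered: "We hypothesize that the use of the tool will reduce healthcare and patient stigma about use of MOUDs".
- **Enrollment and consent, study population.** Both are allocated: "These populations will be randomized to either receipt or no receipt of the shared decision tool".
- **Study procedures, definition of the aid.** "This decision aid is a web-based survey that is presented on a tablet". A later sentence uses the word the same way: "The decision aid survey integrates a values clarification exercise and summarizes patient concerns/preferences to guide shared decision-making with clinicians".
- **Study procedures, randomization.** "Once consent from both parties, patient and provider, is obtained the patient will be randomized to either receive the shared decision aid"; the alternative is the standard-of-care arm. Every control patient should therefore have a consented provider.
- **Study procedures, aid arm.** "If randomized to receive the shared decision aid, the patient and provider will take the survey on separate devices but at the same time".
- **Study procedures, standard-of-care arm.** "If the patient is not randomized to receive the decision aid tool, they will complete the survey and receive standard of care".
- **Study procedures, schedule.** Stigma is measured before discharge and at 2 weeks and 3 months after it. The schedule is given once for each arm, and the respondent is named in neither.
- **Analysis methods.** Likert stigma questions are asked just before and just after the survey, and again at 2 weeks and 3 months. Each result is compared with baseline in pairs, using non-parametric tests. The only comparison between arms is of overall response rates, a term that is not defined.
- **Power.** No sample size is given. The study is described as a pilot.

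**The concern.** The two arm instructions are not parallel. The aid-arm sentence names patient and provider. The control-arm sentence has one pronoun, and whoever completes the survey there also receives standard of care, which fits the patient and not the provider. A coordinator could follow these instructions without ever giving the stigma questions to the provider of a control patient.

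The analysis section would not expose the omission, because a paired test against baseline makes no use of controls. A fall in provider stigma would be credited to the aid when it could come from answering the same questions repeatedly, from giving more acceptable answers once in a study, or from a change of attitude across the hospital over 3 months. An analysis can be rewritten later. Provider scores that were not collected cannot be recovered.

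**Working it through.** The plan states no figure on this point, so there is none to reproduce. The check is a reading of the text, followed by an illustration.

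**1. Who is assigned what**

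| Item | Aid arm | Standard-of-care arm |
|---|---|---|
| Consented provider exists | yes | yes |
| Takes the *survey* | patient and provider, both named | one pronoun, most naturally the patient |
| Stigma before discharge, 2 weeks, 3 months | planned, respondent not named | planned, respondent not named |
| Stigma just before and after the *survey* | has a survey to be timed from | for the provider, no survey is specified to time it from |
| Stigma test | paired against baseline | paired against baseline |

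**2. What *survey* means.** The procedures section uses it for the decision aid. The analysis section places the Likert questions before and after it, so they are a separate instrument. The Summary, however, also speaks of survey assessments of stigma. If *survey* meant the aid in the control-arm sentence, control participants would complete the tool they were randomized not to receive. The word must mean something else there, plausibly the stigma questions, but the text does not say so.

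**3. What each comparison estimates.** Let *e* be the effect of the aid on provider stigma and *d* the change that would occur without it.

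- Paired change in aid-arm providers: *e* + *d*
- Paired change in control-arm providers, if measured: *d*
- Between-arm difference in change: (*e* + *d*) − *d* = *e*

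The planned test addresses *e* + *d*. It is a test of the aid only if *d* = 0.

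**4. Illustration of size.** All inputs are assumptions: 20 or 30 providers per arm, normally distributed change scores with SD 1, *e* = 0, two-sided 5% level, independent providers. The table gives simulated rejection rates for the Wilcoxon signed-rank test on aid-arm providers. Repeated runs agree to within about 2 percentage points.

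| Drift *d* (SD of change) | N = 20 | N = 30 |
|---|---|---|
| 0 | about 5% | about 5% |
| 0.2 | about 13% | about 19% |
| 0.3 | about 24% | about 35% |
| 0.5 | about 54% | about 73% |

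A rank test between arms, with the same N in each arm and drift common to both, rejects about 5% of the time in every row.

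These rates come from using a paired test without controls. Collecting control-provider scores while keeping the paired test as the basis for the conclusion would leave them unchanged.

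**5. A limit on the between-arm comparison.** The procedures section randomizes the patient, and nothing stops one provider from having patients in both arms. If a fraction *f* of control-arm provider records comes from providers who have already used the aid, and its effect carries over in full, the expected difference is (*e* + *d*) − (*f*·*e* + *d*) = (1 − *f*)·*e*. The documents give no basis for a value of *f*.

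**The case against.** A reader might infer that in the control arm only the patient is surveyed, and that there will be no control data on providers. The documents do not support stating that as fact, for four reasons.

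- The aid-arm sentence describes delivery of the decision aid. Naming the provider there does not show that stigma measurement differs by arm.
- The stigma schedule is the same in both arms and is not limited to patients. Timing it from discharge proves nothing about respondents, since the aid arm is timed the same way.
- Consent from both parties before randomization, and the statement that both populations are randomized, suggest that provider data in both arms may be intended.
- The control-arm sentence is too loosely worded to bear a strict grammatical reading.

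All of this stands, and it rules out saying that control providers go unmeasured. It does not supply the missing instruction: no sentence expressly assigns them the stigma questions.

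Two further objections also stand. The N and drift values in the illustration have no basis in the documents. And the inflated rejection rate comes from the paired analysis, which is written for stigma in general, so it affects the patient half of the hypothesis too.

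It can also be said that overall response rates might include stigma responses. The term is undefined and no population is named, so it cannot be counted as a planned comparison of provider stigma. Pilot status excuses low power. It does not turn a change without controls into evidence of preliminary effectiveness.

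**Conclusion.** The point holds in a limited form. The plan does not expressly assign stigma assessments to providers of standard-of-care patients, and it tests stigma only as paired change from baseline. The provider half of the hypothesis therefore has no specified controlled comparison, and any repeat-testing effect or drift would be read as an effect of the aid. Whether control providers would in practice be measured cannot be settled from the text.

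The size cannot be derived from the documents. Under the assumptions shown, with no aid effect, the paired test rejects about 13% (N = 20, drift 0.2 SD) to about 73% (N = 30, drift 0.5 SD) of the time. The between-arm test stays at about 5% provided that providers are independent and drift is the same in both arms. The direction does not depend on those values: any drift towards lower reported stigma favours the aid.

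This should be corrected before enrollment, because the data part cannot be repaired afterwards. The between-arm comparison is the essential part of the correction.

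**What to change.** 1. In the study procedures, replace the control-arm sentence with one that covers both parties. For example: in both arms, the patient and the consented provider each complete the same Likert stigma questions at baseline and at the same later time points; the decision aid is given only in the aid arm.
2. Use *survey* for one instrument only, and give the Likert questions their own name. For the assessment that follows directly after the aid, define a matching time point in the control arm.
3. In the analysis methods, base the provider conclusion on the between-arm difference in change from baseline. Keep the within-arm paired results as description.
4. Reconcile the statement that both populations are randomized with the statement that the patient is. Record a provider identifier and each provider's earlier use of the aid, identify providers with patients in both arms, and specify an analysis that accounts for repeated providers.

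**Cost.** A few minutes of questionnaire for control-arm providers, who have already consented, and some added work to link records by provider. Item 4 is a real limitation: if many providers appear in both arms, exposure to the aid will dilute the between-arm difference, and accounting for repeated providers in the analysis does not fully remove that.

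### The plan makes no allowance for patients who share a prescriber: only a patient code is named, and ordinary paired tests of stigma change would be anti-conservative if prescribers recur

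*Combined protocol and SAP*

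**What the plan says.** The study procedures section enrols patients and prescribers as pairs. Once a patient is interested, "their healthcare provider will be approached for consent as well". Randomisation follows "Once consent from both parties, patient and provider, is obtained", and at that point "the patient will be randomized to either receive the shared decision aid or standard of care". In the aid arm, "the patient and provider will take the survey on separate devices but at the same time". Providers are a study population in their own right, and the hypothesis covers provider stigma as well as patient stigma. All providers must care for patients at the single site and be able to prescribe these medications. No section says whether a provider may take part with more than one patient.

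On identifiers, the same section says the team will "create a unique patient ID code to link participant data and information to rather than their name". No provider code or pair code is mentioned. The limit placed on data collection is worded in terms of health information: "the study team will not collect or record any identifiable health information".

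The analysis summary has stigma measured immediately before and after the survey, at 2 weeks and at 3 months. Of the later measurements it says "These results will be compared to the baseline testing results in a paired manner". The tests are to be non-parametric but are not named. The one between-arm comparison it states is of response rates. No sample size is given, and a power analysis is declined because the study is a pilot.

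**The concern.** The prescriber takes part in the decision-aid session and then in the choice of medication. One prescriber's patients may therefore change in similar ways. Paired non-parametric tests in their usual form, such as the signed-rank test, treat each pair of scores as independent of every other pair. If several pairs come from one prescriber and are positively correlated, the data carry less information than the count of patients suggests. The test then finds change too often.

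This matters here because change from baseline is the only stigma analysis the plan states, and it is to be judged by statistical significance. The provider side has a sharper form of the same problem. If a provider enters with several patients and records are keyed by patient only, one person's stigma scores can appear as several participants. A missing link also has to be dealt with early: once names have been replaced by codes, a pairing that was not recorded may be hard to recover.

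This is separate from carry-over, where a provider who has used the aid then sees a control patient. That is a bias, and modelling correlation would not remove it.

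**Working it through.** **Plan's own figure.** There is none to reproduce: the documents give no sample size, significance level, cluster size or intraclass correlation.

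**Inputs.**
- From the documents: enrolment in pairs, one hospital, no limit of one patient per provider, and paired testing of change from baseline.
- Assumed: two-sided nominal level 0.05 (critical value 1.96); m patients per provider, from 1 to 10; intraclass correlation (ICC) of the change scores within provider, from 0.05 to 0.20. Here m counts only patients in the group being tested. If each arm is tested separately, a provider whose 10 patients split evenly contributes m = 5 to each test.

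**Formulas.** The variance of the mean change is inflated by DE = 1 + (m − 1) × ICC. A test that ignores this has true error 2 × [1 − Φ(1.96/√DE)].

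**Worked example.** For m = 5 and ICC = 0.10, DE = 1 + 4 × 0.10 = 1.4. Then 1.96/√1.4 = 1.656 and the true error is 9.8%.

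| Patients per provider | ICC 0.05 | ICC 0.10 | ICC 0.20 |
|---|---|---|---|
| 1 | DE 1.00, 5.0% | DE 1.00, 5.0% | DE 1.00, 5.0% |
| 2 | DE 1.05, 5.6% | DE 1.10, 6.2% | DE 1.20, 7.4% |
| 5 | DE 1.20, 7.4% | DE 1.40, 9.8% | DE 1.80, 14.4% |
| 10 | DE 1.45, 10.4% | DE 1.90, 15.5% | DE 2.80, 24.1% |

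**Check by simulation.** An ordinary Wilcoxon signed-rank test was applied to normal change scores with no true change, an assumed 40 patients and 4,000 replicates per setting. It rejected in 9.9% at m = 5, ICC 0.10; 14.9% at m = 5, ICC 0.20; and 22.6% at m = 10, ICC 0.20. These agree with the formula to within about 1.5 percentage points.

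**Provider scores.** Repeated change scores from one provider may be more strongly correlated than scores from different patients. At an assumed correlation of 0.5, the formula gives 11.0% for a provider entered twice (DE 1.5) and 25.8% for one entered five times (DE 3.0).

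**Between-arm tests.** The same simulation was run for a rank-sum comparison of arms.
- With patients randomised individually, the error stayed between 4.1% and 5.6% for m from 1 to 10 and ICC from 0 to 0.5, which is close to nominal.
- With providers as the randomised unit, it was 9.2% at m = 5, ICC 0.10, and 25.4% at m = 10, ICC 0.20.

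Which case applies depends on the unit of randomisation, and the documents differ on it. The procedures section randomises the patient. The study-population paragraph of the enrolment section says "These populations will be randomized to either receipt or no receipt of the shared decision tool", after naming both patients and providers.

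**The case against.** The strongest reply is that much of this rests on silence. The code sentence is a confidentiality statement, not a list of database fields. Providers are participants too, and the restriction concerns identifiable health information, which does not bar a coded provider number. The team will know each pairing, because it seeks consent from both parties. A reader might infer that provider correlation cannot be modelled. The documents do not support that; they show only that no provider identifier is specified.

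A reader might also infer that the p-values are wrong. That does not follow either. The tests are unnamed, repeat providers are not documented, and prescribers are to be sought from five clinical groups, so a small pilot could have few patients per provider. With one patient each there is no inflation. The immediate change is measured around a tablet survey, so how far it depends on the provider is unknown.

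Nor should the point be extended to a between-arm stigma test. The plan states none, and under patient-level randomisation such a test is about valid as far as provider correlation goes.

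Finally, this is a pilot, and a model with a provider effect may be hard to fit with few providers.

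These replies limit how firmly the point can be put. They do not remove it: the plan still tests for significance, repeat prescribers at one hospital are plausible, and nothing in the plan would detect or handle them.

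**Conclusion.** The point stands in conditional form. The plan neither specifies a provider identifier nor says how shared prescribers will be handled, and its one stated stigma analysis is of the kind that goes wrong when they occur. The inflation of a nominal 5% test runs from none at one patient per provider to 24.1% at ten patients and an ICC of 0.20, with 7.4% to 14.4% at five. Every one of these figures rests on assumed values of m, ICC and significance level, with equal numbers of patients per provider. The direction is firm for positive correlation; the size is unknown. It is worth correcting because the remedy is cheap and is best put in place before enrolment.

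**What to change.** 1. Before enrolment, give each provider a coded study ID. Store it on every linked patient record and on the provider's own surveys.
2. State whether a provider may take part with more than one patient and, if so, how that provider's repeated surveys enter the analysis.
3. Test change from baseline with a signed-rank test for clustered data, with provider as the cluster. A permutation test that flips signs by whole provider, or a model with a provider effect and a small-sample correction, would also serve. With one patient per provider the clustered signed-rank test reduces to the ordinary one, so nothing is lost if providers do not recur. As this is a pilot, report estimates with intervals ahead of p-values.
4. Reconcile the enrolment and procedures sections on the unit of randomisation, since this decides whether any between-arm test also needs adjusting.

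The cost is one database field, a changed line of analysis code and somewhat wider intervals. Precision will be low if providers are few. For example, with five providers a sign-flip test by provider has a smallest possible two-sided p-value of 2/2⁵ = 0.0625, so it could not reach 0.05.
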